Appendix 2: Classification of Visits Window

Timing of assessment (days relative to Treatment ^a)	Visit	Visit Name to display for Analysis	Study Day (Relative Day) ^a
Weeks -1 to -4	Screening	Screening	-28 ~ -1
Week 0*	Baseline	Baseline (Week 0)	1
Week 4 (± 4 days)	Interim	Interim (Week 4)	29 (25 – 33)
Week 8 (± 4 days)	Interim	Interim (Week 8)	57 (53 – 61)
Week 12 (± 4 days)	EOT	EOT (Week 12)	85 (81 - 89)
4 Weeks Post Last Dose of Study Drug (± 4 days)	Follow-up	Follow-up (4 weeks post last dose of study drug)	28 (24 ~ 32) days after last dose of study drug ^b

* It also depends on Baseline definition of each variable.

a. Day 1 is the day of first dose of treatment.

b. calculate study day (relative day) based on last dose of study drug

Appendix 3: Scoring Details of Efficacy Variables

Alzheimer's Disease COMposite Score (ADCOMs)

ADCOMs score is composite score derived from ADAS-Cog v14, CDR-SOB, and MMSE.

The resultant composite score, ADCOMS, is a weighted linear combination of the remaining individual scale items in the final fitted PLS model using the corresponding PLS coefficients as weighting factors see the table. The range of ADCOMS is between 0 and 1.97. Items making contributions to ADCOMS include 4 items of the ADAS-cog; two items of the MMSE, and all six items of the CDR-SOB.

Items selected in the Wold's PLS model and their corresponding PLS coefficients ⁷

Scale	Item name	PLS coefficients
ADAS-cog	Delayed word recall	0.008
	Orientation	0.017
	Word recognition	0.004
	Word finding difficulty	0.016
MMSE	Orientation time	0.042
	Drawing	0.038
CDR-SB	Personal care	0.054
	Community affairs	0.109
	Home and hobbies	0.089
	Judgment and problem solving	0.069
	Memory	0.059
	Orientation	0.078

ADAS-cog: Alzheimer's Disease Assessment Scale–cognitive subscale; CDR-SB: Clinical Dementia Rating, sum of boxes; MMSE: Mini-Mental State Exam; PLS: partial least squares.

The ADCOMS score, which is rescaled decline, will be derived based on the coefficients and corresponding items selected from PLS regression in above table:

ADCOMs score

$$\begin{aligned}
 &= 0.008 * \textit{Delayed word recall (ADAS - cog)} + 0.017 \\
 &* \textit{Orientation(ADAS - cog)} + 0.004 * \textit{Word recognition(ADAS - cog)} \\
 &+ 0.016 * \textit{Word finding difficulty(ADAS - cog)} + 0.042 \\
 &* \textit{Orientation time(MMSE)} + 0.038 * \textit{Drawing(MMSE)} + 0.054 \\
 &* \textit{Personal care (CDR - SB)} + 0.109 * \textit{Community affairs(CDR - SB)} \\
 &+ 0.089 * \textit{Home and hobbies(CDR - SB)} + 0.069 \\
 &* \textit{Judgement and problem solving(CDR - SB)} + 0.059 \\
 &* \textit{Memory (CDR - SB)} + 0.078 * \textit{Orientation(CDR - SB)}
 \end{aligned}$$

It is careful to use the reversed score with regard to MMSE (maximum score for each item – MMSE score of each item). It means that for the derivation of ADCOMS score, (5- MMSE score of ‘Orientation time’) will be used for ‘Orientation time’ and (1-MMSE score for ‘Drawing’) will be used for ‘Drawing’.

Rey Auditory Verbal Learning Test (RAVLT)

The standard RAVLT format starts with a list of 15 words, which an examiner reads aloud at the rate of one per second. The participant's task is to repeat all the words he or she can remember, in any order. This procedure is carried out a total of five times which can be used for the evaluation of incremental practice effects. Then the examiner presents a second list of 15 words, allowing the participant only one attempt at recall. Immediately following this, the participant is asked to remember as many words as possible from the first list⁸.

The RAVLT test and its score details are given below:

RAVLT	Scoring
Recall List A	Total number of correct words
Recall List B	Number of correct words
Final recall of List A	Number of correct words

Alzheimer's Disease Assessment Scale - Cognitive Behaviour Section (ADAS-Cog v14)

The ADAS-cog v14⁹ includes the following 14 items, with a Total scoring range of 0 – 90.

ADAS Cog Item	Scoring Details
Item 1 - Word Recall Task	
On this task, the participant is given three trials to learn a list of ten high-frequency, high imagery nouns. The ten words are printed in block letters on white cards.
 
Scoring: The participant's score is the mean number of words not recalled across the three trials (maximum score = 10). The score should be calculated to two decimal places. If any of the three trials is not completed for any reason, then the task is considered incomplete and a missing data code must be assigned to the item score.

Item 2 - Naming Objects and Fingers	
For this task, the participant is asked to name 12 randomly presented real objects, with high (flower, bed, whistle, pencil), medium (rattle, mask, scissors, comb) and low (wallet, harmonica, stethoscope, tongs) frequency values. The participant is also asked to name the fingers of his/her dominant hand.
 
Scoring: 0 = 0-2 items (objects and fingers) named incorrectly 1 = 3-5 items (objects and fingers) named incorrectly 2 = 6-8 items (objects and fingers) named incorrectly 3 = 9-11 items (objects and fingers) named incorrectly 4 = 12-14 items (objects and fingers) named incorrectly 5 = 15-17 items (objects and fingers) named incorrectly

Item 3 - Commands	
This task is designed to assess receptive speech. The participant is asked to carry out five separate commands with 1 to 5 steps per command.
 
Scoring: 0 = all commands correct 1 = 1 command incorrect 2 = 2 commands incorrect 3 = 3 commands incorrect 4 = 4 commands incorrect 5 = all 5 commands incorrect

Item 4 - Constructional Praxis	
This test assesses the participant's ability to copy four geometric forms ranging from a very simple one (circle) to a fairly difficult one (cube).
 
Scoring: 0 = all 4 drawings correct 1 = 1 form drawn incorrectly 2 = 2 forms drawn incorrectly 3 = 3 forms drawn incorrectly 4 = 4 forms drawn incorrectly (but one or more side/section of at least one shape drawn) 5 = No figures drawn, no recognizable attempt at drawing any side/section of any figure

Item 5 - Ideational Praxis	
This task is designed to determine whether the participant can perform a familiar but complex sequence of actions.
 
Scoring: 0 = all components performed correctly 1 = failure to perform 1 component

ADAS Cog Item	Scoring Details
	2 = failure to perform 2 components 3 = failure to perform 3 components 4 = failure to perform 4 components 5 = failure to perform 5 components
Item 6 - Orientation	In this task, the participant is asked 8 questions regarding his or her orientation to person, place and time. Scoring: One point is given for each incorrect response (maximum = 8).
Item 7 - Word Recognition Task	On this task the participant is given one trial to learn a list of 12 words. Scoring: There are 24 opportunities for error in the one trial of recognition, including the 12 learning (target) words and 12 distractor words. The participant could incorrectly identify a distractor word as one of the learning words they were just shown, or they could incorrectly say they were not shown a learning word. While all incorrect responses should be noted on the form by the tester (there are 0-24 errors possible in the trial), the maximum error score is 12. If the participant makes 13-24 errors, the score for the trial remains at 12. [name] has stated that the maximum error score is 12 per trial as this is the average number of errors that would be made by a person guessing randomly.
Item 8 - Language	This item is a global rating of the quality of speech, i.e., lack of clarity, difficulty in making oneself understood with words. Scoring: 0 = participant speaks clearly and/or is understandable 1 = very mild: one instance of lack of understandability 2 = mild: participant has difficulty less than 25% of the time 3 = moderate: participant has difficulty 25-50% of the time 4 = moderately severe: participant has difficulty more than 50% of the time 5 = severe: one or two word utterances; fluent, but empty speech; mute
Item 9 - Comprehension of spoken language	This item evaluates the participant's ability to understand spoken language. Scoring: 0 = None: participant understands. 1 = Very Mild: one or two instances of misunderstanding. 2 = Mild: 3-5 instances of misunderstanding. 3 = Moderate: requires several repetitions and rephrasings. 4 = Moderately Severe: participant only occasionally responds correctly; i.e., yes-or-no questions. 5 = Severe: participant rarely responds to questions appropriately; not due to poverty of speech.
Item 10 - word finding difficulty	Along with Spoken Language Ability, this item rates impairment in expressive speech, but it rates only word finding difficulty, whereas Spoken Language Ability is a more global rating of the extent to which the participant can communicate verbally. Scoring: 0=no evidence of word finding difficulty in spontaneous speech 1=very mild: 1 or 2 instances, not clinically significant 2=mild: noticeable circumlocution or synonym substitution 3=moderate: loss of words without compensation on occasion

ADAS Cog Item	Scoring Details
	4=moderately severe: frequent loss of words without compensation 5=severe: nearly total loss of content of words; speech sounds empty; 1-2 word utterances
Item 11 - Remembering Test Instructions	This item evaluates the participant's ability to remember the instructions given for the Word Recognition task only. The score is based on the number of instruction repetitions only after the first two words. No other tasks or aspects of the ADAS-cog are considered when scoring this item. Scoring: 0 = No reminders given in Word Recognition 1 = very mild: reminded once 2 = mild: reminded 2 times 3 = moderate: reminded 3 or 4 times 4 = moderately severe: reminded 5 or 6 times 5 = severe: reminded 7 or more times
Item 12 - Maze	In this task, the participant is asked to find his or her way through a maze with a pencil, without hitting a dead end. The participant is told he or she may pause to make a decision. The task is halted after the participant makes two errors or 240 seconds has elapsed. An example maze is given for practice before the participant attempts the test maze. Scoring: The score is the time to completion or the time at which the participant made the second error (maximum time = 240 seconds). The score from the practice task is not included. The score is calculated only from the timed performance task.
Item 13 - Number Cancellation	In this task, the participant is asked to cross off as many target digits as possible in 45 seconds. Scoring: The score is the number of target items correctly crossed off in 45 seconds, minus the number of incorrectly crossed off items, and minus the number of reminders given. The score from the practice task is not included. The score is calculated only from the timed performance task.
Item 14 - Delayed Recall	If added, this item adds 10 points to the possible total ADAS-cog score. In this task, the participant is asked to recall the 10 words presented during the Word Recall task. There is one trial of recall. This task is administered following completion of the COMMANDS and CONSTRUCTIONAL PRAXIS items. Scoring: The score is the number of words not recalled (Maximum score = 10).
Final	Sum score of 14 items

Clinical Dementia Rating Scale - Sum of Boxes (CDR-SOB)

The CDR-SOB includes the following six items, with a Total scoring range of 0 – 18. Only caregiver/ informant details are to be collected ¹⁰.

CDR	Scoring
Domain 1: Memory Questions	Scoring (0, 0.5, 1, 2, 3) for replies of Informant
Domain 2: Orientation	Scoring (0, 0.5, 1, 2, 3) for replies of Informant
Domain 3: Judgment and Problem Solving	Scoring (0, 0.5, 1, 2, 3) for replies of Informant
Domain 4: Community Affairs	Scoring (0, 0.5, 1, 2, 3) for replies of Informant
Domain 5: Home and Hobbies	Scoring (0, 0.5, 1, 2, 3) for replies of Informant
Domain 6: Personal Care	Scoring (0, 1, 2, 3) for replies of Informant
	Total score = Sum of the Boxes

Mini-Mental Status Examination (MMSE)

The MMSE is a 30-point questionnaire that is used extensively in clinical and research settings to measure cognitive impairment¹¹ and is commonly used in medicine and allied health to screen for dementia. It is also used to estimate the severity and progression of cognitive impairment and to follow the course of cognitive changes in an individual over time; thus making it an effective way to document a participant's response to treatment. The total score range is 0 – 30.

Neuropsychiatric Inventory (NPI)

The NPI was constructed to survey neuropsychiatric disorders in demented patients¹². NPI having 12 domains and For each domain, the relatives assess the frequency of the behaviour (4-point scale), the severity of the symptom (3-point scale) and the emotional stress for the caregiver (6-point scale).

The NPI total score is calculated by multiplying the frequency and severity rates per domain (maximum score per domain is 12) and then calculating the total of 10 domains [domain A to L]. (total NPI-score minimum is 0 and maximum 144). The 12 item score is being used. Total distress is sum of distress of 12 items of the NPI distress questions¹³.

NPI	Scoring
Domain A: Delusions	Score of Frequency (1 - 4), Score of Severity (1 - 3), Distress (0-5)
Domain B: Hallucinations	Score of Frequency (1 - 4), Score of Severity (1 - 3), Distress (0-5)
Domain C: Agitation / Aggression	Score of Frequency (1 - 4), Score of Severity (1 - 3), Distress (0-5)
Domain D: Depression/Dysphoria	Score of Frequency (1 - 4), Score of Severity (1 - 3), Distress (0-5)
Domain E: Anxiety	Score of Frequency (1 - 4), Score of Severity (1 - 3), Distress (0-5)
Domain F: Elation/Euphoria	Score of Frequency (1 - 4), Score of Severity (1 - 3), Distress (0-5)
Domain G: Apathy / Indifference	Score of Frequency (1 - 4), Score of Severity (1 - 3), Distress (0-5)
Domain H: Disinhibition	Score of Frequency (1 - 4), Score of Severity (1 - 3), Distress (0-5)
Domain I: Irritability / Lability	Score of Frequency (1 - 4), Score of Severity (1 - 3), Distress (0-5)
Domain J: Aberrant Motor Behavior	Score of Frequency (1 - 4), Score of Severity (1 - 3), Distress (0-5)
Domain K: Sleep	Score of Frequency (1 - 4), Score of Severity (1 - 3), Distress (0-5)
Domain L: Appetite and eating disorders	Score of Frequency (1 - 4), Score of Severity (1 - 3), Distress (0-5)

Frequency is rated as: 1 - Occasionally - less than once per week; 2 - Often - about once per week; 3 - Frequently - several times per week but less than every day; 4 - Very frequently - daily or essentially continuously present.

Severity is rated as: 1 - Mild - produces little distress in the patient; 2 - Moderate - more disturbing to the patient but can be redirected by the caregiver; 3 - Severe - very disturbing to the patient and difficult to redirect.

Distress is scored as: 0 - no distress; 1- minimal; 2 – mild; 3 – moderate; 4 - moderately severe; 5 - very severe or extreme

Neuropsychological Test Battery (NTB) - Executive Domain (COWAT and CFT)

NTB score is the sum of correct response of Category Fluency Test (CFT) and Controlled Oral Word Association – Test (COWAT). The following scoring table will explain it very clearly.

NTB (COWAT and CFT)	Scoring
COWAT	Total number of correct words
CFT	Total correct responses
	Total incorrect responses
	Total intrusions
Total	COWAT + CFT(Correct response)

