11.1.1.3 Alzheimer’s Disease Assessment Scale - Cognitive Behaviour Section (ADAS-Cog v14)

The ADAS-Cog was developed in the early 1980s in response to the then-perceived lack of appropriate instruments available to test the efficacy of AD drug treatments. It aims to assess the “severity of dysfunction and research in subjects with AD”²⁸. Since its inception, the ADAS-Cog has been used in over 127 AD clinical studies and, although developed specifically for AD, it has frequently been used in non-AD populations, including mild cognitive impairment²⁹. The original ADAS-Cog measures cognitive performance by combining ratings of 11 components (Word Recall, Word Recognition, Constructional Praxis, Orientation, Naming Objects and Fingers, Commands, Ideational Praxis, Remembering Test Instruction, Spoken Language, Word Finding, Comprehension) representing six broad areas of cognition: memory, language, ability to orientate oneself to time, place and person, construction of simple designs, and planning and performing simple behaviours in pursuit of a basic, predefined goal. The ADAS-Cog with 11 items is scored from 0 to 70. The ADAS-Cog v14 was designed to assess cognitive impairment in individuals with early AD. A version of the digit cancellation task was reliable and sensitive to a broad range of dementia severity. Performance on the word learning task with delayed recall and a subset of the mazes task were impaired even in mild AD. As such, these tasks were felt to be useful in studies involving mild or at-risk subjects, as they provide a useful addition to the 11-item version of the ADAS³⁰. Three items (delayed word recall, attention/visual search task, and maze solution) have been added to the ADAS-Cog v11 to assess the participant’s attention and concentration.

This 14-item instrument will be referred to as the ADAS-Cog v14. Total scores of ADAS-Cog 14 range from 0 to 90, with higher scores indicating greater disease severity.

11.1.1.4 Clinical Dementia Rating Scale - Sum of Boxes (CDR-SOB) and Global (CDR Global)

The Washington University CDR is a global assessment instrument that yields global and SOB scores, with the global score regularly used in clinical and research settings to stage dementia severity³¹. The CDR-SOB score has been considered a more detailed quantitative general index than the global score and provides more information than the global CDR score

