7.7.1.1 ADCOMs/ADAS-Cog v14 score

ADCOMs, composite score (0 - 1.97) is derived from ADAS-Cog v14, CDR-SOB, and MMSE. ADAS-Cog v14 score is sum of all 14 items of ADAS-Cog v14. Scoring details for ADCOMs and ADAS-Cog v 14 score are given in Appendix 3.

For analysis of the primary efficacy variables, analysis of covariance (ANCOVA) model will be used to assess the change in ADCOMs/ADAS-Cog v14 score from Baseline (Week 0) to Week 12/EOT. The ANCOVA model will include treatment group as fixed effects and the Baseline value as a covariate.

The primary efficacy hypothesis is:

$$H_0: \mu_P \leq \mu_X$$

$$H_1: \mu_P > \mu_X,$$

where μ_P and μ_X denote the change from Baseline (Week 0) to Week 12/EOT in ADCOMs and ADAS-Cog v14 for the placebo and Xanamem™ treatment groups, respectively. Both tests will be performed at a type I error rate of 0.05 one-sided, with a priori hierarchical handling of multiplicity, based on the least squares means (LS means) for Week 12/EOT. LS means from the ANCOVA will be used to derive 90% and 95% confidence intervals. The primary efficacy analysis will not replace missing Week 12/EOT.

Unless otherwise specified, the ANCOVA will have the following characteristics:

- All subjects in the FAS will be included in the primary efficacy analysis as long as there are both Baseline and valid post-Baseline measurements at Week 12/EOT available.
- The response variable will be the change in ADCOMs score from Baseline (Week 0) to Week 12/EOT visit. Only post-Baseline measurements collected on the EOT will be considered response values.
- The following covariate will be used in the models:
 - Baseline ADCOMs score

- Treatment group
- The following SAS statements will be employed:

```
proc mixed data=xxxx ;
    class <treatment group>;
    model < change ADCOMs score> = <baseline ADCOMs score>
    <treatment group> ;
    lsmeans <treatment group>/ diff cl alpha=0.05;
    lsmeans <treatment group>/ diff cl alpha=0.10;
    ods output lsmean=xxx diffs=xxx;
run;
```

Baseline ADCOMs score, as well as observed and change from Baseline values at post-Baseline visits, will be summarized descriptively.

The analysis described above will be repeated for ADAS-Cog v14. Also analysis will be repeated on PP analysis set for supportive evidence.

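### SAP Appendix 3 adds raw maze seconds and a higher-is-better cancellation count into an ADAS-Cog v14 total said to run from 0 to 90 with higher meaning worse

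*SAP*

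**What the plan says.** SAP 7.7.1.1 defines the endpoint as a plain sum, "ADAS-Cog v14 score is sum of all 14 items of ADAS-Cog v14", and names Appendix 3 as the place where the scoring details are given. Appendix 3 opens its item table by saying that the scale "includes the following 14 items, with a Total scoring range of 0 – 90". Protocol 11.1.1.3 agrees and adds the direction: "Total scores of ADAS-Cog 14 range from 0 to 90, with higher scores indicating greater disease severity".

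The rows of that table for the last timed tasks read differently:

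- **Item 12, maze:** "The score is the time to completion or the time at which the participant made the second error (maximum time = 240 seconds"). The task itself has a stopping rule: "The task is halted after the participant makes two errors or 240 seconds has elapsed".
- **Item 13, number cancellation:** "The score is the number of target items correctly crossed off in 45 seconds, minus the number of incorrectly crossed off items", with the number of reminders also subtracted.
- **Final row:** "Sum score of 14 items".

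Neither document gives a banding, conversion or reversal for items 12 and 13. Where the same appendix needs a reversal, for the two MMSE items in ADCOMs, it writes one out: "It is careful to use the reversed score with regard to MMSE".

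**The concern.** Every other ADAS-Cog item in Appendix 3 is an error count or an impairment rating with a small maximum. Seconds up to 240 and a net count of correct responses are on different scales from these, and the count also runs in the opposite direction. A plain sum of such items cannot be a 0 to 90 score on which higher always means worse.

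The endpoint carries weight. Under Protocol 15.2.2.1, ADAS-Cog v14 is confirmatory if ADCOMs succeeds. Under SAP 9.1 it is part of the interim efficacy test. It is also carried through the multiple-imputation sensitivity analyses (SAP 7.7.1.1) and the subgroup analyses (SAP 7.11), and it is the only basis for the sample size in Protocol 15.1. If the derivation program follows Appendix 3 literally, the maze time would dominate the total, one item would be signed against the alternative hypothesis that placebo change exceeds Xanamem change, and the planning assumptions would refer to a different variable.

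**Working it through.** **1. Room left for items 12 and 13.** Item maxima from SAP Appendix 3:

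| Items | Maximum |
|---|---|
| 1 Word recall | 10 |
| 2, 3, 4, 5 (5 each) | 20 |
| 6 Orientation | 8 |
| 7 Word recognition | 12 |
| 8, 9, 10, 11 (5 each) | 20 |
| Subtotal, items 1 to 11 | 70 |
| 14 Delayed recall | 10 |
| Subtotal, twelve items | 80 |

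The subtotal of 70 matches the 0 to 70 range that Protocol 11.1.1.3 gives for the 11-item scale. A 90-point total leaves 90 − 80 = 10 points for items 12 and 13 together.

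**2. Range as written.** With the maze in seconds, the sum can reach 80 + 240 = 320 before item 13. The maze supplies 240/320 = 75% of that. Item 13 has no stated maximum and can be negative. The stated range of 0 to 90 is not reproduced.

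**3. Direction as written.** Item 13 rises with better performance, so improvement on it raises a total on which a rise is read as decline. The maze has mixed direction, because a participant stopped at the second error is scored at that time. With assumed times for illustration, a maze halted for two errors at 20 s scores 20 and a correct completion at 200 s scores 200. The failure looks better by 180 points, twice the stated range of the whole scale.

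**4. ADCOMs.** Its ADAS-Cog components are delayed recall, orientation, word recognition and word finding, so items 12 and 13 do not enter. Its maximum from the Appendix 3 weights is:

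- ADAS-Cog: 0.008×10 + 0.017×8 + 0.004×12 + 0.016×5 = 0.344
- MMSE: 0.042×5 + 0.038×1 = 0.248
- CDR: 3×(0.054 + 0.109 + 0.089 + 0.069 + 0.059 + 0.078) = 3×0.458 = 1.374
- Total: 1.966, in line with the stated 1.97

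**5. Sample size.** The inputs in Protocol 15.1 are a difference of 2, SD 5, one-sided alpha 0.05 and power 80%. The normal formula gives n = 2 × (1.645 + 0.842)² × 5² / 2² = 77.3, rounded up to 78 per arm. Power at 78 per arm from the noncentral t is 80.0%. For dropout, 156/0.9 = 173.3, rounded up to 174. The plan's figures reproduce on its own inputs.

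**6. What raw seconds could do to power (illustration only).** The documents give no SD for change in maze time. Assume that SD 5 describes the intended 0 to 90 total, hold the difference at 2, ignore item 13, and add an independent maze-change SD of m seconds. The SD is then √(25 + m²), with n = 78 per arm and one-sided alpha 0.05:

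| m (s, assumed) | SD of total | Power |
|---|---|---|
| 0 | 5.00 | 80.0% |
| 2 | 5.39 | 74.7% |
| 5 | 7.07 | 54.5% |
| 10 | 11.18 | 29.7% |
| 30 | 30.41 | 10.8% |
| 60 | 60.21 | 7.5% |

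**The case against.** The strongest reply is that the conversion exists elsewhere. Appendix 3 cites the ADAS administration and scoring manual (SAP reference 9) when it introduces the 14-item table, so the citation covers items 12 and 13. Protocol 11.1.1 says that a study scale binder holds the scoring instructions. Some rows read like text taken from a manual, so items 12 and 13 may simply describe the raw test result. The case report form may capture items that are already converted, in which case a plain sum would give 0 to 90. A raw-seconds total would also breach the stated range visibly, since a maze time above 90 s exceeds it alone, and programming checks would probably catch this. The MMSE contrast is only suggestive, because ADCOMs is a separate composite that mixes scales of opposite direction. The power figures rest on an assumed SD and an unchanged difference of 2.

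Part of this stands. The SAP does point to an external manual for the scale as a whole, nothing shows that any program used raw seconds, and the power table does not measure harm to this trial. But the pointer does not settle the matter. SAP 1.0 says the document provides data derivations, and 7.7.1.1 sends the reader to Appendix 3 for scoring. Appendix 3 does not leave these items to the manual. It states a definite rule for each, and that rule conflicts with its own range.

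**Conclusion.** The concern holds: the ADAS-Cog v14 derivation is wrong as written. The contradiction needs no outside figure. Twelve items account for 80 of 90 points, yet the remaining two are scored so that the sum can reach at least 320, with one item reversed and the maze rewarding early failure. SAP 10.0 declares no change from the protocol's methods, so this is not an announced redefinition of the scale.

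The practical consequence depends on whether the programs follow Appendix 3 literally, which the documents do not show. If they already convert both items, the correction is one of documentation. If they do not, the second primary endpoint is a different and partly reversed variable, and the 2-point difference and SD of 5 cannot be carried over to it. The ADCOMs test is untouched, and there is no arithmetic error in the sample size. Because the rule defines a primary endpoint, it must be corrected before the analysis relies on it.

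**What to change.** In SAP Appendix 3:

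- Replace the raw scores for items 12 and 13 with the point conversion from the study scale binder or the cited scoring manual, both in the higher-is-worse direction and worth 10 points together.
- State how a maze halted for two errors is scored, so that stopping early cannot count as good performance. Converting seconds to points does not settle this by itself.
- Define the ADAS-Cog v14 total as the sum of the converted items, 0 to 90, and align the wording in 7.7.1.1.

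Then check the interim and final derivation programs against the corrected text, and confirm that the SD of 5 in Protocol 15.1 refers to that total. The cost is a few lines of SAP text and a program check, with no new data and no change to the sample size or to ADCOMs.
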